### 8.11.4 Response review

All subjects who meet eligibility criteria and receive at least 1 dose of study medication/undergo 1 scan or procedure will be included in the main analysis of the response rate, even if there are major protocol deviations (e.g., incorrect treatment schedule or drug administration). Each subject will be assigned to one of the following categories:

*Table 5. Categories for Response to Treatment*

Category	Response
1	Complete response
2	Partial response
3	Stable disease
4	Progressive disease
5	Early death from malignant disease
6	Early death from toxicity
7	Early death from other causes

## 9 Unknown (not assessable/insufficient data)

NOTE: By arbitrary convention, category 9 designates unknown status in a clinical database. Subjects in response categories 4 to 9 will be considered to have treatment failure (disease progression).

Conclusions are to be based on the population of all eligible subjects. Subanalyses may be performed on various subsets of subjects, such as those with no major protocol deviations or those who continued in the study for the entire treatment period (i.e., did not withdraw prematurely). Subanalyses will not serve as the basis for drawing conclusions concerning treatment efficacy.

## 9 SAFETY MONITORING AND REPORTING

The PI is responsible for the identification and documentation of adverse events and serious adverse events, as defined below. At each study visit, the PI or designee must assess, through non-suggestive inquiries of the subject or evaluation of study assessments, whether an AE or SAE has occurred.

### 9.1 Adverse Events

An adverse event (AE) is defined as any untoward medical occurrence in a subject administered a study drug and which does not necessarily have a causal relationship with this treatment. An AE can therefore be any unfavorable and unintended sign (including an abnormal laboratory finding), symptom, or disease temporally associated with the use of a study drug, whether or not related to the study drug.

An abnormality identified during a medical test (e.g., laboratory parameter, vital sign, ECG data, physical exam) should be defined as an AE only if the abnormality meets one of the following criteria:

- Induces clinical signs or symptoms.
- Requires active intervention.
- Requires interruption or discontinuation of study medication.
- The abnormality or investigational value is clinically significant in the opinion of the investigator.

All adverse events, whether or not related to the study drug, must be fully and completely documented.

From the first dose of avelumab until 28 days after the last dose of avelumab, or until all serious or study drug-related toxicities have resolved or are determined to be “chronic” or “stable”, whichever is earlier, all AEs must be recorded in the subject medical record and adverse events case report form.

AEs will be assessed according to the CTCAE version 4.0 or the most current version. If CTCAE grading does not exist for an AE, the severity of the AE will be graded as mild (1), moderate (2), severe (3), life-threatening (4), or fatal (5).

Attribution of AEs will be indicated as follows:

- Definite: The AE is clearly related to the study drug
- Probably: The AE is likely related to the study drug
- Possible: The AE may be related to the study drug
- Unlikely: The AE is doubtfully related to the study drug
- Unrelated: The AE is clearly NOT related to the study drug

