## 5.10 Definition of Evaluable Subjects, On Study, and End of Study

Patients who consent but do not receive a dose of study drug will be replaced and will not be considered evaluable.

All subjects enrolled onto the study who receive at least one dose of avelumab will be included in the intention-to-treat analysis for the primary endpoint.

All subjects enrolled onto the study who receive at least one dose of avelumab will be evaluable for the secondary and exploratory endpoints.

Given the potential risk for delayed immune-related toxicities, safety follow-up must be performed 28 days after the last dose of avelumab administration.

The extended safety follow-up beyond 28 days after last study drug administration may be performed either via a site visit or via a telephone call with subsequent site visit requested in case any concerns noted during the telephone call.

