agonists or antagonists. ADT will continue throughout all cycles. If patient has pure SCPC they do not need to be started on ADT but are allowed to continue per treating provider if already on ADT. Concurrent enzalutamide is permitted.

9. **Study Treatment (Avelumab):** Avelumab will be administered at 10 mg/kg IV every 2 weeks. One cycle is 2 infusions (4 weeks).
10. **Tumor imaging:** Bone scan, and either CT or MRI scans of the chest, abdomen, and pelvis will be performed to assess disease status at baseline as well as every 8 weeks or at treatment discontinuation (if imaging did not occur within 6 weeks of visit ) as well as whenever disease progression is suspected, to confirm partial or complete response. NaF-PET/CT may be used in place of bone scan and CT in select cases. In all cases, the same imaging modality should be used throughout the study on individual subjects. Baseline tumor imaging must be performed within 35 days of cycle 1 day 1. MRI brain should be done in all subjects at baseline if indicated clinically and should be followed every 8 weeks with the other scans if metastasis(es) are found or if disease progression is suspected. Allowable window for tumor assessment imaging studies is +/- 7 days. Subjects removed from therapy for any reason other than disease progression will continue to be followed for radiographic progression until additional treatments are started, when available.
11. **Post-Progression Biopsy:** An optional standard of care post-treatment progression biopsy will also be collected and additional tissue for research will be banked in the Biospecimen Repository & Processing Core (BRPC) under Pro00080869 for future research on resistance mechanisms including assessment of immune checkpoint status.
12. **Physical Examination:** Examination of major body systems. It does **not** need to be done cycle 1, day 1 if performed within the last 7 days.
13. **Adverse Events:** Subjects must be followed for adverse events from the first day of study treatment until 28 days after the last dose of study treatment, or until all serious or study drug-related toxicities have resolved or are determined to be “chronic” or “stable”, whichever is earlier. Serious adverse events should be monitored and reported from the time the patient starts study drug treatment as described in the protocol.

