## 8.6 Follow up period

### 8.6.1 Safety Follow-up visit

The safety follow-up visit is to occur 28 days (+/- 7 days) after the last dose of study agent. Subjects that discontinue treatment due to reasons other than progressive disease will be followed until progression through Standard of Care scans.

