### 8.6.2 Extended safety follow-up

Given the potential risk for delayed immune-related toxicities, extended safety follow-up must be performed up to 90 days after the last dose of avelumab administration for all serious or study drug-related toxicities were not resolved or not determined to be “chronic” or “stable” within 28 days after the last dose of avelumab. The extended safety follow-up beyond 28 days after last study drug administration may be performed either via a site visit or via a telephone call with subsequent site visit requested in case any concerns noted during the telephone call.

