### **8.8.2 Follow-up Requirements for Early Withdrawal**

Upon early withdrawal from study treatment, an end of treatment visit should be conducted within 7 days as described above. At withdrawal, all on-going study-related toxicities and SAEs should be followed until resolution, unless in the investigator's opinion, the condition is unlikely to resolve due to the subject's underlying disease. Subjects should be followed up for new AEs for 90 calendar days after the last dose of avelumab. All new AEs possibly related to study treatment occurring during that period should be collected.

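### The 28-day AE recording rule (9.1, schedule footnote 13) is not reconciled with the 90-day rules (8.8.2, 8.6.2), and no scheduled contact asks about new AEs after the safety visit

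*Combined protocol and SAP*

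**What the plan says.** **The 28-day rule.** Section 9.1 (Adverse Events) starts recording at the first avelumab dose. It gives two possible ends: 28 days after the last dose, or the point at which serious or drug-related toxicities have resolved or been judged chronic or stable. It then says "whichever is earlier, all AEs must be recorded in the subject medical record and adverse events case report form". Footnote 13 of the schedule of events applies the same two ends and the same earlier-of clause to follow-up: "Subjects must be followed for adverse events from the first day of study treatment until 28 days after the last dose of study treatment".

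**The 90-day rules.** Section 8.8.2, on early withdrawal, says "Subjects should be followed up for new AEs for 90 calendar days after the last dose of avelumab" and "All new AEs possibly related to study treatment occurring during that period should be collected". Section 8.6.2 says "extended safety follow-up must be performed up to 90 days after the last dose of avelumab administration", but only for serious or drug-related toxicities not settled by day 28.

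**The contacts.** Section 5.10 says "safety follow-up must be performed 28 days after the last dose of avelumab administration" and allows further safety contact by visit or telephone, with no date or trigger. Section 8.6.1 says "The safety follow-up visit is to occur 28 days (+/- 7 days) after the last dose of study agent". Section 9 ties AE inquiry to visits: "At each study visit, the PI or designee must assess" whether an event has occurred. In the schedule, the AE row is marked on Day 1 and Day 15 of each cycle, at end of treatment and at the safety visit. It is blank under long-term follow-up. Footnote 15 and section 8.7 make that follow-up a survival check every 3 months, counted from the end-of-treatment visit, by telephone or chart review and without a study clinic visit.

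**The analysis.** Safety is secondary objective 4. Section 11.6.2 summarises it descriptively and names no AE window.

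**The concern.** Sections 5.10 and 8.6.2 both justify safety follow-up by the risk of late immune-related toxicity. A late toxicity may first appear after day 28. A site working from 9.1 and the schedule would not record it, while a site working from 8.8.2 would be expected to collect it. No section says which applies, or to whom.

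The population of 8.8.2 is also unclear. Treatment has no fixed length (5.1, 11.4), so every man stops for some reason. Section 8.5 deals with stopping at progression, and 8.8.1 lists reasons for early withdrawal that overlap with it only in part. A man who stops at iRECIST progression may or may not be an early withdrawal.

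At stake is whether the late part of the safety profile in secondary objective 4 is collected on one rule. Stage 1 has a single site, so the question there is which rule that site applies. Differences between sites can arise only in stage 2.

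**Working it through.** The plan states no figure on this point, so there is none to reproduce. The check sets the rules side by side and counts the days between contacts.

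**1. The rules compared**

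| Section | Which events | Which men | Latest end after last dose |
|---|---|---|---|
| 9.1 | all AEs, recorded | all dosed | day 28, or earlier |
| Footnote 13 | all AEs, followed | all dosed | day 28, or earlier |
| 8.8.2 | new AEs followed; possibly related ones collected | early withdrawal from treatment | day 90 |
| 8.6.2 | serious or related toxicities open at day 28 | men who have one | day 90 |

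The four rows can be satisfied together: record all AEs to day 28, go on collecting possibly related new AEs to day 90, and follow open toxicities to day 90. That layering is the reader's construction. Because 9.1 takes the earlier of its two ends, its literal wording makes day 28 the last day of recording.

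**2. Two test cases**

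- *A non-serious, possibly related AE that first appears on days 29 to 90.* Section 9.1 does not record it. Section 8.6.2 does not reach it, because it was not open at day 28. Section 9.3 does not reach it, because it is not serious. Section 8.8.2 requires its collection if the man counts as an early withdrawal. The schedule has no AE assessment at which to find it.
- *A related toxicity open at day 28.* Section 9.1 ends recording, while 8.6.2 continues follow-up with a contact route. Its outcome is partly covered by 8.8.2 (follow-up to resolution), by 9.3 for serious events, and by the instruction in 10.2.2 to keep case report forms up to date.

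The first case is the real exposure.

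**3. Days without a scheduled AE inquiry**

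Inputs: safety visit at day 28 ± 7 (8.6.1); 90-day period (8.8.2).

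- Safety visit: 28 − 7 = day 21 to 28 + 7 = day 35.
- Late visit: 90 − 35 = 55 days; 55/90 = 61%.
- Early visit: 90 − 21 = 69 days; 69/90 = 77%.
- With an early visit, the last 28 − 21 = 7 days of the 28-day window also come after the final AE inquiry.

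The first long-term contact is 3 months, about 91 days, after the end-of-treatment visit. It therefore falls near or past day 90 after the last dose, and it asks about survival.

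**4. Scale in the summary**

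One man counted or not moves a percentage by at most 1/49 = 2.0 points if 49 are dosed, or 1/18 = 5.6 points if 18 are. The change is zero if he already has an event in that category. The documents give no rate of new events on days 29 to 90, so the number of men affected cannot be derived.

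**The case against.** The strongest reply is that the windows cover different things: all AEs to day 28, possibly related new ones to day 90, unsettled toxicities to day 90. On that view there is no contradiction, only a missing cross-reference. The layering is available and the reply is right that far. What stands is that the protocol never states it, that 9.1 read literally stops before it, and that the schedule does not carry it out.

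There are also partial routes to late events. Section 5.10 allows contact beyond day 28 and is not confined to open toxicities. Section 8.6.3 leaves imaging and clinic visits to standard of care. Medical history, which includes concomitant illnesses, is marked at long-term follow-up and could look back. Section 9.3 sets no end date for reporting serious events to the lead site, and sends suspected-related ones to the drug supplier at any time after the last dose. A separate data and safety monitoring plan (12.6) was not available for this review. Each route is optional, undated, not marked as an AE assessment, or dependent on the investigator already knowing of the event. None is a scheduled inquiry about new AEs.

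Four stronger readings are tempting and are not supported:

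- *Recording could stop during treatment once a toxicity resolves.* The literal clause allows this, but the AE row covers every treatment visit and section 9 requires inquiry at each one. It is a drafting fault with little practical effect on treatment.
- *Events are lost for 55 to 69 days.* That is the gap between contacts, not a count of missed events.
- *Late serious events go unreported.* Section 9.3 largely covers them once known.
- *The accrual-suspension rule in 5.3 is compromised.* It applies at any time and classifies each patient by worst toxicity. With no window named, the natural reading is that any known related event of grade 3 or higher counts.

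**Conclusion.** The point holds in a limited form and should be corrected. The 28-day and 90-day rules are not reconciled, and following 9.1 and the schedule as written does not deliver what 8.8.2 requires. For 55 to 69 days of the 90-day period there is no scheduled inquiry about new AEs.

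The consequence is confined mainly to new, non-serious, related events on days 29 to 90 in the descriptive safety summary. Its size in events is unknown. The primary response endpoint and the stage 1 response decision are not affected.

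This rests on three assumptions: that the schedule table as read shows every marked AE assessment; that the separate monitoring plan does not already set an AE contact after the safety visit; and that the optional contact in 5.10 is not routinely made for all men.

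**What to change.** The change concerns data collection only. Reconcile 5.10, schedule footnote 13, 8.6.2, 8.8.2 and 9.1 into one AE recording rule.

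1. Remove or correct the resolution limb and its earlier-of clause in 9.1 and footnote 13, so that all AEs are recorded at least to day 28.
2. State one window, confirmed by the sponsor, and the subjects it covers, for case report form recording of new possibly related AEs and of the outcome of toxicities open at day 28. The protocol already uses 90 days in 8.6.2 and 8.8.2.
3. Add a matching AE entry to the schedule, using the telephone route already allowed in 5.10 and 8.6.2.
4. Use the same window for the safety summary in 11.6.2.

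The cost is wording in five places, one schedule entry, one sentence in 11.6.2, and one extra telephone contact for men not already in extended follow-up. Reported toxicity may rise slightly, and some late events will be harder to attribute, for example after a man has started another treatment. The change is best made early, because events never asked about may not be recoverable later.

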## 9.2 Serious Adverse Events

An AE is considered “serious” if, in the view of either the investigator or sponsor, it results in any of the following outcomes:

- Results in death,
- Is life threatening (an AE is considered “life-threatening” if, in the view of either the investigator or sponsor, its occurrence places the subject at immediate risk of death. It does not include an AE that, had it occurred in a more severe form, might have caused death.)
- Results in persistent or significant disability/incapacity or substantial disruption of the ability to conduct normal life functions,
- Results in congenital anomaly, or birth defect,
- Requires inpatient hospitalization or leads to prolongation of hospitalization (hospitalization for treatment/observation/examination caused by AE is to be considered as serious),
- Other medically important events.

## 9.3 Reporting of SAEs

Serious adverse events, whether or not considered drug related, should be reported to the lead site/sponsor (Duke) within 24 hours of becoming aware of the event, using the provided DCI SAE Report Form and the SAE Review Form (Site Assessment). These documents should be sent to:

**The DCI Safety Desk – [contact]; [contact]; email: [[contact]](mailto:[contact])**

If the safety desk cannot be reached within 24 hours, the Principal Investigator should be contacted: [name] ([contact]; [contact]; email: [[contact]](mailto:[contact])).

The initial report for each SAE or death should include at minimum the following information:

- Protocol # and title
- Patient initials, study identification number, sex, age
- Date the event occurred (onset)
- Description of the SAE
- Dose level and cycle number at the time the SAE occurred
- Description of the patient’s condition
- Indication whether the patient remains on study
- Causality

Follow-up information including severity, action taken, concomitant medications, and outcome should be communicated to Duke as soon as possible.

Upon receipt of the Serious Adverse Event Reporting form by the DCI Safety Desk, the PI will be notified and be required to complete the PI assessment of the DCI Safety SAE Report Review Form. The DCI safety desk will, in turn, submit the SAE to the DUHS IRB if deemed reportable by the PI assessment. The DCI safety desk will also report the event to Pfizer as described below.

The following reportable events must be submitted to Pfizer within 24 hours (or immediately for death or life-threatening events) using the DCI SAE Report Form with *the Pfizer Reportable Events Fax Cover Sheet* with each SAE submission.

- **Serious Adverse Events**
- **Exposure during Pregnancy or Breastfeeding (even if not associated with an adverse event)**
- **Occupational exposure (even if not associated with an adverse event)**
- **Potential drug-induced liver injury (Hy's Law cases): These events are considered important medical events and should be reported as SAEs.**

The DCI SAE Report Form with the Pfizer Reportable Events Fax Cover Sheet should be emailed or faxed to:

Pfizer U.S. Clinical Trial Department  
 Email: [[contact]](mailto:[contact])  
 [contact]

The following minimum information is required:

- Protocol
- Site / PI
- Subject number, sex and age
- The date of report
- A description of the SAE (event, seriousness of the event)

Follow-up information for the event should be sent within promptly (within 7 days) as necessary.

In addition, if Principal Investigator becomes aware of an SAE occurring any time after the administration of the last dose of the Pfizer Product, Principal Investigator should report that SAE to Pfizer if the Principal Investigator suspects a causal relationship between the Pfizer Product and the SAE.

#### **Reporting to the FDA**

The Sponsor-Investigator (Duke) is responsible for reporting the serious adverse event to the FDA in accordance with 21CFR 312.32. Any SAE that is possibly related and unexpected must be submitted to the FDA attached to the IND.

## **9.4 Emergency Unblinding of Investigational Treatment**

Not applicable

## **9.5 Procedure in case of pregnancy**

Not applicable, only men will be enrolled in this study.

## **9.6 Safety Oversight Committee (SOC)**

The Duke Cancer Institute SOC is responsible for annual data and safety monitoring of DUHS sponsor-investigator phase I and II, therapeutic interventional studies that do not have an independent Data Safety Monitoring Board (DSMB). The primary focus of the SOC is review of safety data, toxicities and new information that may affect subject safety or efficacy. Annual safety reviews includes but may not be limited to review of safety data, enrollment status, stopping rules if applicable, accrual, toxicities, reference literature, and interim analyses as provided by the sponsor-investigator. The SOC in concert with the DCI Monitoring Team oversees the conduct of DUHS cancer-related, sponsor-investigator therapeutic intervention and prevention intervention studies that do not have an external monitoring plan, ensuring subject safety and that the protocol is conducted, recorded and reported in accordance with the protocol, standing operating procedures (SOPs), Good Clinical Practice (GCP), and applicable regulatory requirements.

## 10 QUALITY CONTROL AND QUALITY ASSURANCE

### 10.1 Monitoring

This clinical research study will be monitored both internally by the PI and institutionally by the Duke Cancer Institute (DCI). In terms of internal review the PI will continuously monitor and tabulate adverse events. Appropriate reporting to the Duke University Medical Center IRB will be made. If an unexpected frequency of Grade III or IV events occur, depending on their nature, action appropriate to the nature and frequency of these adverse events will be taken. This may require a protocol amendment, dose de-escalation, or potentially closure of the study. The PI of this study will also continuously monitor the conduct, data, and safety of this study to ensure that:

- Interim analyses occur as scheduled;
- Stopping rules for toxicity and/or response are met;
- Risk/benefit ratio is not altered to the detriment of the subjects;
- Appropriate internal monitoring of AEs and outcomes is done;
- Over-accrual does not occur;
- Under-accrual is addressed with appropriate amendments or actions;
- Data are being appropriately collected in a reasonably timely manner.

DCI review and monitoring of this protocol occurs in accordance with the NCI-approved Data and Safety Monitoring Plan. Briefly, protocol review begins with an initial review by the Cancer Protocol Committee (CPC), which assesses the ethics and safety of the protocol. Documentation of these assessments will be maintained. Formal, independent monitoring will be conducted by the DCI Monitoring Team after the first 3 subjects are enrolled, followed by annual monitoring of 1-3 subjects until the study is closed to enrollment and subjects are no longer receiving study interventions that are more than minimal risk. DCI Monitoring Team reports and additional data/safety/toxicity reports submitted by the PI will be reviewed by the Safety Oversight Committee (SOC) on an annual basis. Additional monitoring may be prompted by findings from monitoring visits, unexpected frequency of serious and/or unexpected toxicities, or other concerns. Monitoring visits may also be initiated upon request by DUHS and DCI Leadership, CPC, SOC, the Duke Office of Audit, Risk and Compliance, a sponsor, an investigator, or the IRB. All study documents must be made available upon request to the DCI Monitoring Team and other authorized regulatory authorities, including but not limited to the National Institute of Health, National Cancer Institute, and the FDA. Every reasonable effort will be made to maintain confidentiality during study monitoring.

